3.6.3 Additional safety assessments

3.6.3.1 *Laboratory variables, vital signs*

The following laboratory variables and vital signs variables will be analyzed. They will be converted into standard international units.

- Hematology:
 - Red blood cells and platelets: hemoglobin, hematocrit, platelet count
 - White blood cells: leukocytes, neutrophils, lymphocytes, monocytes, basophils, eosinophils

- Clinical chemistry:
 - Metabolism: glucose, albumin, lipase, amylase
 - Electrolytes: sodium, potassium, chloride, calcium corrected, bicarbonate, magnesium
Calcium Corrected (mmol/L) = Total calcium (mmol/L) + 0.8 * 0.25 * [4 – Serum albumin (g/L) * 0.1]
 - Renal function: creatinine, estimated glomerular filtration rate (eGFR), blood urea nitrogen.
 - Liver function: alanine aminotransferase, aspartate aminotransferase, alkaline phosphatase, lactate dehydrogenase, bilirubin
- Vital signs: heart rate, systolic and diastolic blood pressure, respiratory rate, temperature, Eastern Cooperative Oncology Group (ECOG) Performance status

Data below the lower limit of quantitation/detection limit (LLOQ) will be replaced by half of the LLOQ, data above the upper limit of quantification will be replaced by upper limit of quantification (ULOQ) value.

For hematological parameters and some selected biochemistry parameters, Sanofi sponsor generic ranges (lower limit of normal [LLN], upper limit of normal [ULN]) are defined and will be used for grading (see list of parameters in [Section 5.4](#)). For other biochemistry parameters, grading will be derived using local laboratory normal ranges.

Quantitative analyses

When relevant, for laboratory variables and vital signs above, descriptive statistics for results and changes from baseline will be provided for the last value and the worst value (minimum and/or maximum value depending on the parameter) during the on-treatment period. These analyses will be performed using local measurements for laboratory variables.

Analyses according to potentially clinically significant abnormality (PCSA) and NCI grading

For laboratory variables, analyses according to NCI grading will be made based on NCI-CTCAE version 5.0. In addition, for eGFR, blood urea nitrogen, hematocrit, monocytes, basophils, and chloride, PCSA analyses will be performed based on the PCSA list currently in effect at Sanofi at the time of the database lock.

Analyses according to PCSA and NCI grading will be performed based on the worst value during the treatment-emergent period, using all measurements (either local or central, either scheduled, nonscheduled or repeated).

For laboratory variables and vital signs above, the incidence of participants with at least one PCSA during the treatment-emergent period will be summarized regardless of the baseline level and according to the following baseline status categories:

- Normal/missing
- Abnormal according to PCSA criterion or criteria

For laboratory variables graded by NCI-CTCAE,

- The number (%) of participants with abnormal laboratory tests at baseline will be presented by grade.
- The number (%) of participants with abnormal laboratory tests during the treatment-emergent period will be summarized by grade. When appropriate, the number (%) of participants with abnormality of any grade and with Grade 3-4 abnormalities will be provided.

3.7 OTHER ANALYSES

3.7.1 Other variables and/or parameters

3.7.1.1 PK analyses

No PK parameters will be assessed, as only sparse sampling for pharmacodynamic concentrations of SAR444245 is implemented in the study.

Table 8 - List of PK concentrations and definitions

PK concentrations	Definition	Sparse PK SAR444245	Sparse PK Cetuximab
C_{through}	Concentration observed just before intervention administration during repeated dosing		X
C_{EOI}	Concentration at end of infusion	X	X
C_{D2}	Concentration taken any time at day 2 after previous administration	X	

Applicable concentrations for SAR444245 (C_{EOI} , C_{D2}) and for Cetuximab (C_{through} , C_{EOI}) will be described on the PK population for each planned visit using the following descriptive statistics: mean, geometric mean, median, standard deviation, coefficient of variation, minimum, and maximum. These analyses will be performed by specific subgroups (eg, gender, body mass index [BMI], age) if appropriate.

All concentration values below the lower limit of quantitation (LLOQ) will be treated as zero in all summary statistics. Geometric mean will not be computed in case at least one concentration is below LLOQ.

3.7.1.2 Immunogenicity analyses

Participant's ADA status, response variable and kinetics of ADA responses (see definitions below) will be summarized on the ADA population.

Kinetics of ADA responses will be described for participants with treatment-induced ADA and for participants with treatment-boosted ADA, separately. Time to ADA onset and duration of ADA will be described with minimum, Q1, median, Q3 and maximum statistics.

Peak titer will be described with minimum, Q1, median, Q3 and maximum statistics for participants with treatment-induced ADA and for participants with treatment-boosted ADA, separately.

ADAs against SAR444245 (negative, positive, inconclusive) and corresponding titers, ADAs directed against PEG moiety of SAR444245 status (negative, positive) and ADAs cross-reacting with endogenous IL-2 status (negative, positive) will also be described overtime using descriptive statistics.

ADAs directed against PEG moiety of SAR444245 status and ADAs cross-reacting with endogenous IL-2 status will only be determined if ADAs against SAR444245 status is positive.

The impact of positive immune response on efficacy, PK and safety variables may be further explored, depending on ADA incidence.

Participant's ADA status against SAR444245

- Participants with **pre-existing ADAs** correspond to participants with ADAs present in samples drawn before first administration of intervention. Participants with missing ADA sample at baseline will be considered as without pre-existing ADA.
- Participants with **treatment-emergent ADA** correspond to participants with at least one treatment-induced/boosted ADA.
 - Participants with **treatment-induced ADAs** correspond to participants with ADAs that developed during the treatment-emergent (TE) period and without pre-existing ADA (including participants without pre-treatment samples).
 - Participants with **treatment-boosted ADAs** correspond to participants with pre-existing ADAs that are boosted during the TE period to a significant higher titer than the baseline. A 2-fold serial dilution schema is used during titration, so at least a 4-fold increase will be considered as significant.
- Participants with **unclassified ADA** correspond to participants with pre-existing ADAs that cannot be classified as treatment-boosted ADA because of missing titer(s) (ie, a positive ADA sample during the TE period in a participant with pre-existing ADA but with missing titer at this sample or at baseline).
- Participants **without treatment-emergent ADA** correspond to participants without treatment-induced/boosted ADA and without any inconclusive sample nor unclassified ADA during the TE period.
- Participants **with inconclusive ADA** are defined as participants which cannot irrefutably be classified as with or without treatment-emergent ADA.

Kinetics of ADA response

[figure not shown]
Kinetics of ADA response will be derived for participants with treatment-induced/boosted ADA considering ADA samples collected during the TE period and post-treatment period.

- **Time to onset of ADA response** is defined as the time period between the first IMP administration and the first treatment-induced/boosted ADA.
- **Duration of ADA response** is defined as the time between the first treatment-induced/boosted ADA and the last treatment-induced/boosted ADA, irrespective of negative samples or positive samples not reaching the boosted threshold in-between. ADA duration will be summarized only for participants with persistent ADA response.
 - A positive sample (boosted positive sample for participants with pre-existing ADA) occurring after the TE period will be considered as treatment-induced/boosted ADA if a previous treatment-induced/boosted ADA occurred during the TE period and less than 16 weeks before this sample.
- **Persistent ADA response** is defined by treatment-induced/boosted ADA with a duration of ADA response of at least 16 weeks.
- **Transient ADA response** is defined by treatment-induced/boosted ADA with a duration of ADA response of less than 16 weeks and the last sample of the TE period is not treatment-induced/boosted.
- **Indeterminate ADA response** is defined by treatment-induced/boosted ADA that are neither persistent nor transient.

ADA response variable:

- **ADA incidence** is defined as the proportion of participants found to have seroconverted (treatment-induced ADAs) or boosted their pre-existing ADA response (treatment-boosted ADAs) at any time point during the TE period.
- **Incidence of ADAs directed against PEG moiety of SAR444245** is defined as the proportion of participants with ADAs directed against PEG moiety of SAR444245 during the TE period among evaluable participants. Participants from ADA population are evaluable for ADAs directed against PEG moiety except if ADAs directed against PEG moiety status is not determined on an ADA against SAR444245 positive sample.
- **Incidence of ADAs cross-reacting with endogenous IL-2** is defined as the proportion of participants with ADAs directed against endogenous IL-2 during the TE period among evaluable participants. Participants from ADA population are evaluable for ADAs directed against endogenous IL-2 except if their status is not determined on an ADA against SAR444245 positive sample.

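### The anti-PEG and IL-2 cross-reacting ADA incidences count any positive result on treatment, so they are prevalences on a different basis from overall ADA incidence

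*SAP*

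**What the plan says.** SAP Section 3.7.1.2 lists three measures under the ADA response variable, and all three are called incidence.

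- Overall ADA incidence "is defined as the proportion of participants found to have seroconverted (treatment-induced ADAs) or boosted their pre-existing ADA response", at any time in the treatment-emergent (TE) period.
- Anti-PEG incidence "is defined as the proportion of participants with ADAs directed against PEG moiety of SAR444245 during the TE period among evaluable participants".
- The incidence of antibodies cross-reacting with endogenous IL-2 "is defined as the proportion of participants with ADAs directed against endogenous IL-2 during the TE period among evaluable participants".

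The same section defines pre-existing ADA: these participants "correspond to participants with ADAs present in samples drawn before first administration of intervention". For such a participant to count as boosted, the titer must rise enough: "A 2-fold serial dilution schema is used during titration, so at least a 4-fold increase will be considered as significant". A participant with no baseline ADA sample is treated as having no pre-existing ADA.

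On typing, the section says that anti-PEG status and "ADAs cross-reacting with endogenous IL-2 status will only be determined if ADAs against SAR444245 status is positive". The trigger is therefore any ADA-positive sample, not only an induced or boosted one. Specificity is recorded as negative or positive; titers are named only for total ADA against SAR444245.

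On evaluability, everyone in the ADA population is evaluable for a specificity unless that specificity was left undetermined on a sample positive for ADA against SAR444245.

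**The concern.** The SAP separates antibodies brought into the trial from those that arise or rise on treatment, and applies that separation to overall ADA incidence and to onset, duration and persistence. The two specificity measures leave it out. A participant who enters with PEG-reactive ADA and stays positive at the baseline titer is not a case for ADA incidence but is a case for anti-PEG incidence.

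A reader will take these figures as showing whether treatment provokes antibodies to the PEG moiety or to endogenous IL-2. As defined, they show how many participants had such antibodies on treatment, whatever their origin. Specificity is determined only on ADA-positive samples, so a reader also expects its incidence to be no larger than ADA incidence. A larger figure would look like a data error.

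The evaluability wording raises a second question: whether a participant with a positive specificity result stays in the analysis when another ADA-positive sample has no result.

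**Working it through.** The SAP gives no anti-PEG or IL-2 incidence figure, so there is none to reproduce. The check compares the definitions and then sizes the gap by arithmetic. The only SAP number used is the planned cohort size of about 40 (Section 4). All rates and counts below are assumptions, and all 40 are taken to be in the ADA population.

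**1. One participant traced through the definitions.** ADA is positive at baseline and PEG-positive. On treatment, ADA stays positive, the total titer rises less than 4-fold, and the sample is PEG-positive.

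- Overall ADA incidence: not induced and not boosted, so not a case.
- Anti-PEG incidence: PEG-positive in the TE period, so a case.

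The IL-2 item behaves in the same way. The data handling conventions in Section 5.5 do not change this.

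**2. Size of the gap.** Let *pre* be the proportion carrying the specificity before treatment, all still positive on treatment. Let *b* be the share of carriers whose total ADA is boosted, and *ind* the induced rate in the rest.

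- As written: pre + (1 − pre) × ind
- Induced/boosted basis, as for ADA incidence: pre × b + (1 − pre) × ind
- Difference: pre × (1 − b), whatever the induced rate

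With b = 10% and, for display, ind = 5%:

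| pre | As written | Induced/boosted basis | Difference (points) | Participants of 40 |
|---|---|---|---|---|
| 0% | 5.0% | 5.0% | 0 | 0 |
| 5% | 9.75% | 5.25% | 4.5 | 1.8 |
| 10% | 14.5% | 5.5% | 9.0 | 3.6 |
| 20% | 24.0% | 6.0% | 18.0 | 7.2 |
| 30% | 33.5% | 6.5% | 27.0 | 10.8 |

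**3. Can the specificity figure exceed ADA incidence?** Take 4 participants with treatment-induced ADA, 2 of them PEG-positive, and 6 unboosted PEG-positive carriers.

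- ADA incidence: 4/40 = 10%
- Anti-PEG incidence as written: (2 + 6)/40 = 20%
- Anti-PEG among induced cases only: 2/40 = 5%

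So it can. The counts were chosen to show that it is possible, not that it is likely.

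**4. Evaluability, read literally.** One untyped ADA-positive sample removes the participant, with no exception for a positive result on another sample and no restriction to the TE period. An untyped baseline positive would therefore also exclude. Take 6 PEG-positive participants of 40, of whom 2 also have one untyped ADA-positive sample.

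- As written: (6 − 2)/(40 − 2) = 4/38 = 10.5%
- Positives kept: 6/40 = 15.0%

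Suppose each ADA-positive sample of such a participant is untyped with probability *u*, independently, and every typed one is positive. With *m* samples, the share of shown positives that is dropped is [1 − (1 − u)^m − u^m]/(1 − u^m).

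- m = 2: 9.5% at u = 5%, 33.3% at u = 20%
- m = 3: 14.3% at u = 5%, 48.4% at u = 20%

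This tends to pull the rate down, because only ADA-positive participants can be excluded while ADA-negative ones always stay in the denominator. The carrier effect in step 2 pushes it up.

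**The case against.** The measures are descriptive, Section 3.5 plans no testing, and no decision rule in the SAP uses them. The definitions are explicit and reproducible, and on-treatment positivity of any origin is a legitimate quantity, so the fault could be seen as a label. Section 3.7.1.2 also describes PEG and IL-2 status over time and summarizes participants by ADA category, so baseline positivity would plausibly be visible by visit.

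Much of this stands. It limits the consequence and makes renaming an acceptable remedy. It does not remove the mismatch: summaries by visit do not show which participants in the numerator were already positive, and the incidence line would be read on its own.

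Three stronger readings are tempting, and the document does not support them.

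- *That the immunogenicity secondary endpoint is compromised.* It is not. The endpoint in Section 1.2 is incidence of ADA against SAR444245, and its definition rests on induced or boosted ADA. The two specificity measures are not among the visible endpoints.
- *That shown positives will certainly be dropped.* That follows only from the literal wording. The IL-2 sentence can be read as referring to the participant's overall status, so that someone is non-evaluable only when no sample settles it. This reading is possible but not written, so the rule needs clarifying. The SAP also says nothing about how typing results go missing, so a heavier loss among persistent responders is an assumption.
- *That counting specificity only on induced or boosted samples cures the problem.* Boosting is defined on total ADA titer. A participant PEG-positive at baseline whose total titer rises 4-fold because of other antibodies would still count as incident. One with PEG-negative pre-existing ADA who turns PEG-positive without a 4-fold total rise would be missed.

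**Conclusion.** The point holds as a mismatch of definitions. The anti-PEG and IL-2 incidences are TE-period prevalences, count unboosted pre-existing carriers as incident, and are not on the same basis as ADA incidence in the same list. This follows from the wording and needs no assumption.

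The size does need assumptions. The SAP gives no pre-existing prevalence. The excess is zero with no carriers, and 4.5 to 27 percentage points for an assumed prevalence of 5% to 30%, if 10% are boosted and all remain positive. The evaluability problem is conditional on the literal reading and on some ADA-positive samples being untyped. Where both effects occur they tend to oppose each other, so the reported figure alone would not show the net direction.

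The correction is worth making because it is cheap and the figures would otherwise be misread. No test, decision rule or listed secondary endpoint changes.

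**What to change.** Change Section 3.7.1.2 as follows.

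1. **Incidence.** For each specificity, count a participant with a positive result in the TE period who was ADA-negative or specificity-negative at baseline. Handle a missing baseline ADA sample as the section already does, as no pre-existing ADA.
2. **Baseline-positive participants.** Report those who were specificity-positive at baseline and remain positive on a separate line, split by whether total ADA was boosted. The split is the most that can be done, because a boost of the PEG or IL-2 component cannot be derived from a positive/negative status.
3. **Evaluability.** Keep any participant with a qualifying positive TE result. Exclude only those with an untyped ADA-positive TE sample and no positive specificity result, or with an untyped ADA-positive baseline sample that leaves a positive TE result unclassifiable. List the latter separately.

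An alternative to items 1 and 2 is to keep the present numerator, rename it TE-period prevalence, and show baseline status beside it. The evaluability rule should be clarified in either case.

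The cost is SAP wording, one or two dataset flags, and a small unclassified group; no new samples are needed. Under item 1 a participant with specificity-negative pre-existing ADA who turns specificity-positive without a 4-fold rise in total titer is incident for the specificity but not for overall ADA. The specificity figure is therefore still not strictly a subset of ADA incidence, and a table footnote should say so.

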3.7.1.3 Biomarker analyses

3.7.2 Subgroup analyses

Analyses will be performed on the primary endpoint across the following subgroups (categories with fewer than 5 participants may be combined with other categories):

Table 9 - Subgroup analyses

	A1	A2	B1	B2
Number of prior systemic therapy regimens (0 versus 1-2)			Yes	Yes
LDH laboratory results at baseline (normal versus abnormal)	Yes	Yes	Yes	Yes
Histopathology subtype at baseline (Squamous cell carcinoma or other)	Yes	Yes	Yes	Yes
Location at baseline (Hypopharynx, Larynx, Oral Cavity, Oropharynx, Tonsil, or other locations)	Yes	Yes	Yes	Yes
PD-L1 status at baseline (<1% versus $\geq 1\%$)	Yes	Yes		

The ORR will be provided, as well as the corresponding 90% CI, for each subgroup, using the same method as applied to the primary analysis.

3.8 INTERIM ANALYSES

No formal interim analyses are planned. However, at the end of the safety run-in part (cohort A2 only), the occurrence of DLT and other safety data will be reviewed by Study Board (SB) to confirm safe dose for further continuation.

After the dose is confirmed by the SB, the cumulative safety data for each study intervention across cohorts will be reviewed periodically by the DMC. The enrollment will not be paused or stopped during the safety monitoring unless severe safety concern arises. DMC will review safety data periodically. Ad hoc DMC meetings may also be held if a significant safety issue or an issue deemed important for discussion arises on this or other SAR444245 studies. The DMC procedures will be detailed in the DMC charter and approved by the DMC members.

In addition, for each cohort, in order to support project strategic planning and design of future studies, informal interim analysis(es) may be conducted during the dose expansion part of the study, eg, after 20 participants have undergone at least 2 post-baseline tumor assessments or have discontinued the study intervention, whichever is earlier.

The cohort cut-off for the primary ORR endpoint analysis corresponds to approximately 9 months from the date of the last participant's first infusion (to document that last participant response is maintained for 6 months).

For each cohort, the cut-off date for the final analysis (ie, analysis of secondary objectives and update of primary objective) will be 3 years from cohort last patient-in (LPI).

3.9 CHANGES TO PROTOCOL-PLANNED ANALYSES

This section summarizes major statistical changes in the protocol amendment(s).

Major statistical changes in protocol amendment(s)

Amendment Number	Approval Date	Changes	Rationale
3	22/12/2021	1.1 Synopsis, 3 Objectives and Endpoints: Table 2, 9.4.3.1 Time to response, and 9.4.3.2 Duration of response Definitions of Time to response and Duration of response have been revised as follows: 
• Time to response (TTR) defined as the time from the first administration of investigational medicinal product (IMP) to the first tumor assessment at which the overall response was recorded as PR or CR that is subsequently confirmed and determined by investigator per RECIST 1.1.• Duration of response (DoR), defined as the time from first tumor assessment at which the overall response was recorded as PR or CR that is subsequently confirmed until documented progressive disease (PD) determined by investigator per RECIST 1.1 or death from any cause, whichever occurs first.	For clarification

Amendment Number	Approval Date	Changes	Rationale
3	22/12/2021	1.1 Synopsis and 9.4.3.5 Adverse Events Analyses of adverse events (AEs) related to specific IMP have been removed as treatment-related treatment-emergent adverse events (TEAEs) will be analyzed overall, regardless of the drug.	To assess treatment-related AE of the regimen as whole (SAR444245 with other anticancer therapies)
3	22/12/2021	9.3 Populations for Analyses The efficacy population definition was revised to "All participants from the exposed population with at least one evaluable post-baseline tumor assessment or who permanently discontinued study treatment".	To characterize the efficacy excluding participants newly enrolled
3	22/12/2021	9.4.3.6 Clinical laboratory evaluations and 9.4.5 Other safety analyse(s) Descriptive statistics for laboratory variables and vital signs will be performed only when relevant. The following text was deleted: "These analyses will be performed using local measurements for laboratory variables".	These analyses will be done as needed following analyses of abnormalities according to NCI-CTCAE grade
3	22/12/2021	9.4.5 Other safety analyse(s) "ECG" was removed from quantitative analyses.	ECG data are not collected systematically during the treatment period
3	22/12/2021	10.9 Appendix 9: Response evaluation criteria in solid tumors (RECIST) 1.1 "Or progressive disease" has been removed from the sentence "Confirmatory scans should also be obtained at least 4 weeks following initial documentation of objective response or progressive disease".	To correct a typographical error

